8.11.5 Precautions

Adverse events should be treated in accordance with standard medical practice. During the course of the study, the overall safety, and tolerability of all study treatments will be reviewed by the sponsor and the investigator.

8.11.6 Reporting of Adverse Events Associated with Study Drug Overdose, Misuse, Abuse or Medication Error

AEs associated with study drug overdose, misuse, abuse, and medication error refer to AEs associated with uses of the study drug outside of that specified by the protocol. Overdose, misuse, abuse, and medication error are defined as follows:

Overdose: Accidental or intentional use of the study drug in an amount higher than the protocol-defined dose

Misuse: Intentional and inappropriate use of study drug not in accordance with the protocol

Abuse: Sporadic or persistent intentional excessive use of study drug accompanied by harmful physical or psychological effects

Medication error: Any unintentional event that causes or leads to inappropriate study drug use or subject harm while the study drug is in the control of site personnel or the subject.

All AEs associated with overdose, misuse, abuse, or medication error should be captured on the Adverse Event eCRF and also reported using the procedures detailed in Reporting of SAEs even if the AEs do not meet serious criteria. Abuse is always to be captured as an AE. If the AE associated with an overdose, misuse, abuse, or medication error does not meet serious criteria, it must still be reported using the SAE form and in an expedited manner but should be noted as non-serious on the SAE form and the Adverse Event eCRF.

8.12 Concomitant Medications and Concomitant Therapies

Any medication (including OTC medications) taken by a subject within 30 days prior to the Screening Visit and during the course of the study and the reason for use of the medication will be recorded on the eCRF. Upon entering the study, each subject will be instructed to report the use of any medication (including OTC medications) to the investigator.

Any radiation therapy (linear beam or seeds) taken by the subject within 30 days prior to the Screening Visit and during the course of the study, including type of treatment, and duration of the treatment will be recorded on the eCRF.

8.13 Prohibited Medications

The following medications are prohibited with the appropriate washout period, if any, for each prohibited medication:

- Retroviral/antiretroviral medications, except for remdesivir
- Any experimental drug/clinical trial, except for remdesivir and convalescent plasma

8.14 Withdrawal of Subjects

All subjects reserve the right to withdraw from the study at any time. The investigator will encourage all subjects who decide to withdraw from the study to complete all evaluations which may be necessary to assure that the subject is free of untoward effects and to seek appropriate follow-up for any continuing problems.

- a. Any subject who withdrawals consent will be withdrawn from the study.
- e. Any subject who is lost-to-follow-up will be withdrawn from the study.

The investigator will withdraw any subject from the study if, in the investigator's opinion, it is not in the subject's best interest to continue.

The date the subject is withdrawn from the study and the reason for discontinuation will be recorded on the case report form. When a subject fails to return for scheduled study visits, the investigator will make a reasonable effort to contact the subject and determine why the subject failed to return. This information will be documented on the study records. When a subject is withdrawn from the study (regardless of the reason), all evaluations required at the final study visit should be performed.

9.0 STATISTICAL ANALYSIS

9.1 Sample Size Calculation

In the Phase 2, there are no power calculations done to determine the sample size. The Phase 2 study is intended as a proof-of-concept study only.

9.2 **Populations**

Intent-to-Treat (ITT) population: All enrolled subjects who have taken at least one dose of study drug. The ITT population will be used as the safety population.

Modified Intent-to-treat (MITT) population: All enrolled subjects who have taken at least 7 doses of study drug.

9.3 Efficacy Analyses

A statistical analysis plan will be written for this Phase 2 clinical study. A detailed description of the analyses that will be conducted will be included in that document.

9.3.1 Primary Endpoint

The primary endpoint for the study will be the proportion of subjects that are alive without respiratory failure at Day 29. Respiratory failure is defined endotracheal intubation and mechanical ventilation, extracorporeal membrane oxygenation, high-flow nasal cannula oxygen delivery, noninvasive positive pressure ventilation, clinical diagnosis of respiratory failure with initiation of none of these measures only when clinical decision making is driven solely by resource limitation.

This analysis will compare the percentage of subjects that are alive without respiratory failure on Day 22 (responder). The percentage of subjects that meet these criteria in each of the two treatment groups will be summarized and compared observationally and statistically.

The number and percentage of responders will be summarized by treatment group. Responders will be analyzed using a logistic regression model. This model will include treatment as a factor and study site and WHO Ordinal Scale for Clinical Improvement at baseline as a covariates. Odds ratios, standard errors, 95% confidence intervals and p-values for the treatment difference will be presented.

The primary analysis will be performed on the ITT population. Subjects for whom respiratory failure and/or vital status at Day 29 cannot be established will be excluded from the analysis, noting that the number of such subjects is expected to be minimal. A sensitivity analysis will be performed treating these subjects as non-responders. A further sensitivity analysis also be performed on the mITT population.

9.4 Secondary Analyses

Full details for the handling of missing data, and consideration of subjects that die during the study for those endpoints that do not directly incorporate death, will be included in the Statistical Analysis Plan.

9.4.1 Secondary Endpoints

9.4.1.1 Mean change from baseline in WHO Ordinal Scale for Clinical Improvement at Day 15, Day 22 and Day 29

The mean change in WHO Ordinal Scale for Clinical Improvement from baseline to Day 22 and from baseline to Day 29 will be assessed.

The worst category recorded on Day -1 will be baseline and the worst category recorded on Day 22 and Day 29 of the study will be used in this analysis.

Descriptive statistics (n, mean, standard deviation, median, minimum and maximum) will be summarized for absolute values, and change from baseline by treatment group and visit.

Change from baseline will be analyzed using mixed model for repeated measures (MMRM) including treatment, visit and treatment-by-visit interaction as fixed effects and study site and WHO Ordinal Scale for Clinical Improvement at baseline as covariate. The resulting F-tests will be based on Kenward-Roger's adjusted degrees of freedom. Least squares means, standard errors, 95% confidence intervals and p-values for treatments and treatment differences at each visit will be presented.

9.4.1.2 Proportion of subjects that are Grade 5, 6, 7, or 8 on the WHO Ordinal Scale for Clinical Improvement at Day 15, Day 22, and Day 29

Proportion of subjects that are Grade 5, 6, 7, or 8 on the WHO Ordinal Scale for Clinical Improvement at Day 15, Day 22, and Day 29 will be assessed. This analysis will compare the percentage of subjects that have NOT progressed to a WHO Ordinal Scale for Clinical Improvement score of 5, 6, 7, or 8 (responder) on Day 15, Day 22 or Day 29. The worst category on each day of the study will be used in this analysis. The percentage of subjects that meet these criteria in each of the two treatment groups will be summarized and compared observationally and statistically.

This endpoint will be analyzed using the same methodology as for the primary endpoint.

9.4.1.3 Proportion of subjects with normalization of fever and oxygen saturation through Day 15, Day 22, and Day 29.

The percentage of subjects with normalization of fever and oxygen saturation through Day 15, Day 22 and Day 29 (inclusive) will be summarized. A subject will be considered as a treatment success if fever normalization maintained for at least 24 hours AND peripheral capillary oxygen saturation (SpO₂) >94% sustained for 24 hours is observed.

This analysis will compare the percentage of subjects that meet the composite endpoint of fever normalization maintained for at least 24 hours AND peripheral capillary oxygen saturation (SpO₂) >94% sustained for 24 hours is observed (responder) at Day 15, Day 22, and Day 29. The percentage of subjects that meet these criteria in each of the two treatment groups will be summarized and compared observationally and statistically.

This endpoint will be analyzed using the same methodology as for the primary endpoint.

9.4.1.4 Days on mechanical ventilation

Days on mechanical ventilation will be summarized using descriptive statistics (n, mean, standard deviation, median, minimum and maximum) by treatment group. Treatment comparison will be based on analysis of covariance (ANCOVA) model including treatment as a factor and study site and WHO Ordinal Scale for Clinical Improvement at baseline as covariates. Treatment difference, standard error, 95% confidence interval and p-value will be presented.

9.4.1.5 All-cause mortality at Day 15, Day 22, and Day 29

The number and percentage for all-cause mortality will be summarized by treatment group and timepoint.

This endpoint will be analyzed using the same methodology as for the primary endpoint.

All-cause mortality will be analyzed by comparing the survivor functions between treatment arms using Kaplan-Meier methodology. Proportion of mortality and 95% confidence intervals at Day 15, Day 22 and Day 29 will be reported. Log-rank test will be performed to test the homogeneity of survival curves between the treatment groups. Cox's proportional hazards model will be fitted to assess the significance of the differences between treatment arms. Model will include term for treatment and WHO Ordinal Scale for Clinical Improvement at baseline as covariate.

9.4.1.6 Proportion of patients alive and free of respiratory failure at Day 15, and Day 22

The percentage of subjects alive and free of respiratory failure through Day 15, and Day 22 (inclusive) will be summarized.

This analysis will compare the percentage of subjects that are alive and free of respiratory failure (responder) at Day 15, and Day 22. The percentage of subjects that meet these criteria in each of the three treatment groups will be summarized and compared observationally and statistically.

This endpoint will be analyzed using the same methodology as for the primary endpoint.

9.4.1.7 Proportion of patients alive and discharged from the ICU at Day 15, Day 22, and Day 29

The percentage of subjects alive and discharged from the ICU through Day 15, Day 22 and Day 29 (inclusive) will be summarized.

This analysis will compare the percentage of subjects that are alive and discharged from the ICU (responder) at Day 15, Day 22, and Day 29. The percentage of subjects that meet these criteria in each of the two treatment groups will be summarized and compared observationally and statistically.

This endpoint will be analyzed using the same methodology as for the primary endpoint.

9.4.1.8 Proportion of patients alive and discharged from hospital at Day 15, Day 22, and Day 29

The percentage of subjects alive and discharged from the hospital through Day 15, Day 22 and Day 29 (inclusive) will be summarized.

This analysis will compare the percentage of subjects that are alive and discharged from the hospital (responder) at Day 15, Day 22, and Day 29. The percentage of subjects that meet these criteria in each of the two treatment groups will be summarized and compared observationally and statistically.

This endpoint will be analyzed using the same methodology as for the primary endpoint.

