8.7 Day 29 ± 3 days

The following assessments will be performed at approximately Day 29 (\pm 3 days):

- 1. Vital Signs (temperature/pulse/supine blood pressure)
- 2. SpO₂
- 3. Physical examination (including weight)
- 4. 12-lead ECG (single)
- 5. Chest X-ray or CT scan
- 6. Clinical Laboratory tests
 - a. Hematology (Appendix A)
 - b. Serum chemistry (Appendix A)
 - c. Urinalysis
- 7. Adverse events
- 8. Record the usage of any concomitant medications and ongoing treatments.
- 9. Assessment of primary and secondary endpoints
- 10. Pregnancy test

8.8 Follow up visits at Day 45 (± 3 days) and Day 60 (± 3 days) (can be conducted via phone/teleconference)

- 1. Adverse events
- 2. Assessment of primary and secondary endpoints (observational assessment)

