#### 6.12.2.4 Days on mechanical ventilation

Mechanical ventilation is defined as subject having 'Intubation and mechanical ventilation' or 'Ventilation + additional organ support – pressors, RRT, ECMO'.

'Days on mechanical ventilation' will be summarized using descriptive statistics (n, mean, standard deviation, median, minimum and maximum) by treatment group.

'Days on mechanical ventilation' will be the number of days on mechanical ventilation up to Day 29. If subject dies early in the study and was on mechanical ventilation at the time of the death then it is assumed that subject was on mechanical ventilation up to Day 29. A sensitivity analysis will be performed assigning the worst possible endpoint score for deaths (i.e., considered to be on mechanical ventilation from baseline up to Day 29 and setting days on mechanical ventilation to 29).

Treatment comparison will be based on analysis of covariance (ANCOVA) model including treatment as a factor, and study site, remdesivir use (No/Yes), dexamethasone use (No/Yes) and WHO Ordinal Scale for Clinical Improvement at baseline as covariates. Treatment difference, standard error, 95% confidence interval and p-value will be presented.

Example SAS codes for the analysis are as follows:

#### 6.12.2.5 All-cause mortality at Day 15, Day 22, and Day 29

The number and percentage for all-cause mortality will be summarized by treatment group and visit.

These endpoints will be analyzed using the same methodology as for the primary endpoint.

Responders are subjects who are alive at the time of the visit.

Non-responders are subjects who died before the visit.

Separate analysis will be performed for each visit.

QMD Ref: Worldwide-TMP-ST-005-7.0 Effective: 12Aug2019	Governing QMD: Worldwide-SOP-ST-001	
Confidentiality Statement		
This document is the property of Worldwide Clinical Trials Inc. and may not be duplicated, copied, altered or removed from company without		
prior approval from Worldwide Quality Assurance or in compliance with Worldwide Standard Operating Procedures		

Worldwide Clinical Trials Controlled Quality Management Document		
WORLDWIDE CLINICAL TRIALS	Sponsor:	Veru Inc.
	Protocol Number:	V0211901
STATISTICAL ANALYSIS PLAN. PHASE 2-3-4		

Responder rates and differences between treatment groups in responder rates will be calculated as sensitivity analysis using the same methodology as for the primary endpoint.

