#### 9 CHANGES TO PLANNED PROTOCOL ANALYSIS

In the statistical models the use of remdesivir and dexamethasone were added as covariates.

QMD Ref: Worldwide-TMP-ST-005-7.0 Effective: 12Aug2019	Governing QMD: Worldwide-SOP-ST-001	
Confidentiality Statement		
This document is the property of Worldwide Clinical Trials Inc. and may not be duplicated, copied, altered or removed from company without		
prior approval from Worldwide Quality Assurance or in compliance with Worldwide Standard Operating Procedures.		

prior approvation in our moralistic quantity insolutation of the compliance with insolutation of the compliance of the c

Worldwide Clinical Trials Controlled Quality Management Document					
WORLDWIDE CLINICAL TRIALS	Sponsor:	Veru Inc.			
CLINICAL TRIALS	Protocol Number:	V0211901			
STATISTICAL ANALYSIS PLAN. PHASE 2-3-4					

Secondary endpoint 'Proportion of subjects that are Grade 5, 6, 7, or 8 on the WHO Ordinal Scale for Clinical Improvement at Day 15, Day 22, and Day 29' will be excluded from the SAP as it would be the same as primary endpoint and corresponding endpoints for Days 15 and 22.

Interim analysis will not be performed.

ITT Population was updated to include all randomized subjects regardless whether the subject too study drug or not. This will not have impact on the populations as all randomized subjects were treated.

Efficacy Evaluable (EE) Population was added.

QMD Ref: Worldwide-TMP-ST-005-7.0 Effective: 12Aug2019

Governing QMD: Worldwide-SOP-ST-001

Worldwide Clinical Trials Controlled Quality Management Document					
WORLDWIDE CLINICAL TRIALS	Sponsor:	Veru Inc.			
CLINICAL TRIALS	Protocol Number:	V0211901			
STATISTICAL ANALYSIS PLAN. PHASE 2-3-4					

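### The protocol's Kaplan-Meier, log-rank and Cox analyses of mortality are absent from the SAP, and the SAP does not record or justify their removal

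*Protocol*

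**What the plan says.** Protocol 9.4.1.5 (all-cause mortality at Days 15, 22 and 29) sets out two strands. The first is the logistic method of the primary endpoint, which Protocol 9.3.1 defines with treatment, study site and baseline WHO score. The second is a survival analysis: "All-cause mortality will be analyzed by comparing the survivor functions between treatment arms using Kaplan-Meier methodology", with "Proportion of mortality and 95% confidence intervals at Day 15, Day 22 and Day 29 will be reported". It continues "Log-rank test will be performed to test the homogeneity of survival curves between the treatment groups" and "Cox's proportional hazards model will be fitted to assess the significance of the differences between treatment arms". The Cox model has treatment and baseline WHO score only.

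SAP 6.12.2.5 keeps the first strand, separately for each visit: "These endpoints will be analyzed using the same methodology as for the primary endpoint". Outcome is binary: "Non-responders are subjects who died before the visit", and everyone alive at the visit is a responder. It adds unadjusted responder rates and differences by the primary-endpoint sensitivity method. SAP 6.12.1 specifies Wald intervals and tests for that method, and its code also requests Barnard's exact test. The survival strand does not appear.

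SAP Section 9 lists the changes from the protocol. On models it says only "In the statistical models the use of remdesivir and dexamethasone were added as covariates".

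On follow-up, Protocol 8.11.4 collects SAEs, which include deaths, to 60 days after first dose. Protocol 8.8 schedules at Days 45 and 60 "Assessment of primary and secondary endpoints (observational assessment").

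**The concern.** A between-arm mortality analysis that the protocol specifies is missing from the SAP, and the place where the SAP declares such changes is silent. A reader of the study report who holds the protocol will look for survival curves and a log-rank p-value and find neither, with no stated reason.

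The analyses that remain discard information. A death on Day 16 and a death on Day 21 count the same, and a subject whose vital status becomes unknown contributes nothing up to the last contact, where Kaplan-Meier would use that time. Deaths from Day 30 to Day 60 enter no mortality comparison.

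**Working it through.** Neither document gives a mortality rate, an expected number of deaths or a power figure, so there is no figure of the plan to reproduce. The core of the point is a comparison of texts.

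**1. Protocol against SAP**

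| Item | Protocol 9.4.1.5 | SAP 6.12.2.5 and Section 11 |
|---|---|---|
| Logistic regression | Yes (treatment, site, baseline WHO) | Yes, with remdesivir and dexamethasone added; Table 14.2.5.2 |
| Counts and percentages | Yes | Yes; Table 14.2.5.1 |
| Rate difference, Wald and Barnard | No | Added; Table 14.2.5.2a |
| Kaplan-Meier with Day 15, 22, 29 estimates | Yes | Absent; no table or figure |
| Log-rank test | Yes | Absent |
| Cox model | Yes | Absent |

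SAP Section 9 names five changes: the two added covariates, the dropped WHO Grade 5 to 8 endpoint, the cancelled interim analysis, the ITT definition and the new EE population. It includes the ITT change even while saying that it has no effect. The removal of the survival analyses is not among them. The amendment table at the front of the SAP records an addition to 6.12.2.5 and no deletion.

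**2. Deaths after Day 29**

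- The mortality section covers Days 15, 22 and 29 only.
- Later deaths appear in the listing of deaths (14.3.2.1), which is not a comparison.
- The TEAE window (SAP 6.15.1) closes 7 days after last dose, so by about Day 28 for a subject dosed to Day 21, and earlier for one discharged earlier. Fatal events with later onset miss the by-arm serious TEAE tables.
- The only between-arm model that reaches Days 45 and 60 is the MMRM of the WHO score (SAP 6.12.2.1). Its LOCF rule carries forward the last observation before or at death, so it need not register the death.

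**3. How fragile is the retained logistic model?**

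The plan gives 40 subjects, 20 per arm. The following are assumptions: 3 to 8 sites; remdesivir use 60%; dexamethasone use 70%; baseline WHO 3/4/5/6 in 10/50/30/10%; and the death risks shown. With site as a class variable the model has 4 + (sites − 1) terms besides the intercept, so 6 for 3 sites and 11 for 8. Simulation, 800 trials per scenario:

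| Assumed deaths (one arm v other) | Mean deaths | Separation somewhere in the model | Treatment odds ratio not finite |
|---|---|---|---|
| 30% v 30% | 12.4 | 23% to 94% | 1% to 3% |
| 20% v 10% | 6.5 to 6.8 | 58% to 99% | 13% to 28% |
| 10% v 5% | 3.2 to 3.4 | 90% to 100% | 53% to 66% |

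With site as one linear term (5 sites), the last column becomes 0%, 12% and 41%.

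The chance that an arm of 20 has no deaths is (1 − p)^20: 0.95^20 = 0.358 and 0.90^20 = 0.122. In that case neither the logistic odds ratio nor the Cox hazard ratio is finite. Barnard's test still gives a result: 0 v 4 of 20, p = 0.039; 1 v 5, p = 0.107; 1 v 6, p = 0.049.

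**4. What the log-rank test would add**

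Schoenfeld's approximation, two-sided 5%, 1:1 allocation: power = Φ(|ln HR| × √d / 2 − 1.96), where d is the number of deaths. For d = 8 and HR = 0.5: 0.693 × 2.828 / 2 − 1.96 = −0.98, so power is 16%.

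| Deaths (assumed) | HR 0.5 | HR 0.3 |
|---|---|---|
| 4 | 10% | 23% |
| 8 | 16% | 40% |
| 12 | 22% | 55% |

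**The case against.** The SAP still has a usable mortality comparison. It keeps counts by arm, adds rate differences, and its code requests an exact test that needs no covariate model. A reader might infer that the SAP has replaced survival analysis with a logistic model that will often fail. The documents do not support that. The logistic regression was already in the protocol, and the two added covariates are disclosed. How often separation occurs turns on site count and death rates that are not given. The example code for that model is not shown in the text available, so the coding of site, and any penalised or exact option, cannot be seen. Separation in a site term also need not make the treatment odds ratio infinite. All of this stands.

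A reader might also infer that stopping at Day 29 departs from the protocol. It does not: the protocol names mortality only at Days 15, 22 and 29, sets no horizon for the curves, and calls the Day 45 and 60 assessment observational.

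Nor do the documents show selective reporting. They do not say when or why the analyses were left out.

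Two further points carry weight. Protocol 9.3.1 has a rule for unknown vital status in the primary analysis (exclude, with a non-responder sensitivity analysis) and expects few such subjects. If so, Kaplan-Meier and crude proportions at Day 29 will nearly agree, though the SAP does not restate the rule. And SAP 6.12.4 treats all secondary endpoints as descriptive.

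None of this explains the missing survival analyses or their absence from Section 9.

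**Conclusion.** The point holds as an unrecorded departure from the protocol on a secondary endpoint. Kaplan-Meier, log-rank and Cox are planned in Protocol 9.4.1.5, absent from SAP 6.12.2.5 and the output list, and not declared in Section 9. This part needs no assumption.

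The practical loss is moderate: time of death, censored follow-up, and any by-arm view of deaths between Day 30 and Day 60. It is not the loss of a decisive test. At 4 to 12 deaths the log-rank test has 10% to 22% power at a hazard ratio of 0.5. The primary endpoint is unaffected.

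Separation in the logistic model is a real possibility at 40 subjects, but its frequency is not established. The chance of a non-finite treatment odds ratio runs from 0% to 66% across the assumed scenarios and is high only when deaths are very few. It supports having an analysis that does not depend on that model. It does not show that the retained set of analyses will fail.

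**What to change.** In SAP 6.12.2.5 and Section 11, restore the protocol's Kaplan-Meier curves by arm with estimates and 95% intervals at Days 15, 22 and 29, and the log-rank test. State the time origin and the horizon of the test, and censor at the date last known alive; discharge alone should not censor a subject who is contacted later. Keep the Cox model (treatment, baseline WHO score) as supportive only, and say that no finite hazard ratio exists if one arm has no deaths.

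As an addition beyond the protocol, carry the curves and the by-arm death counts to Day 60 descriptively.

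In Section 9, list and justify anything from Protocol 9.4.1.5 that is still dropped.

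The cost is about one table, one figure and a few lines of code, on data already collected. The downside is one more low-powered p-value, which should be labelled descriptive in line with SAP 6.12.4.
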